 - i. The study duration is three weeks. The subjects will be required to have either OMT, BEMER, OMT+BEMER, or Placebo treatments during the course of the study. Each subject in the OMT groups (i.e. OMT and OMT+BEMER) will receive treatment 3 times per week for a period of 3 weeks. Subjects in the BEMER groups (i.e. BEMER and OMT+BEMER) will receive treatment 5 times per week for a period of 3 weeks. Finally, subjects in the Placebo group will receive the light touch and BEMER sham treatments at same intervals as the corresponding experimental groups. OMT, BEMER, and placebo treatments will be performed by osteopathic medical students who have completed additional training given by a licensed osteopathic physician, to ensure uniform technique.
- b. Recruitment:

- i. LECOM-Bradenton faculty, staff, osteopathic medical, dental, pharmacy, and master's students will be informed via email of the opportunity to participate in the research study and will be given contact information to confirm eligibility with a study coordinator (Appendix A).

c. Experimental Sessions

- i. Following written consent (Appendix B), subjects will be given a randomized study ID number. They will be randomized into their treatment group.
- ii. Each subject in the OMT groups (i.e. OMT and OMT+BEMER) will receive treatment 3 times per week for a period of 3 weeks. As previously mentioned, subjects in the BEMER groups (i.e. BEMER and OMT+BEMER) will receive treatment 5 times per week for a period of 3 weeks. Finally, subjects in the Placebo group will receive the light touch and BEMER sham treatments at same intervals as the corresponding experimental groups. OMT, BEMER, and placebo treatments will be performed by osteopathic medical students who have completed additional training given by a licensed osteopathic physician, to ensure uniform technique. All treatments will be performed during the span of three consecutive weeks.
- iii. Subjects will complete brief questionnaires regarding low back pain and quality of life before the beginning of study and will complete the same questionnaires following the completion of the three week treatment (Appendices C, D, E).

III. Analysis

a. Study Statistics

- i. Primary outcome variable
 1. Questionnaire ratings before and after treatments
- ii. Statistical plan including sample size justification and interim data analysis
 1. Paired T-tests (N~10 subjects) to investigate the changes in low back pain after each treatment protocol.

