 2. One-Way ANOVA to investigate any statistically significant differences between the means of each of the 4 experimental groups.
- iii. Early stopping rules
 1. Any adverse effect, as determined by the attending licensed osteopathic physician. No adverse effects are anticipated.

b. Blinding

- i. All outcome analyses will be performed in a blinded fashion. Subject survey and corresponding data will be de-identified and analyzed retrospectively by investigators with no exposure to the treatment sessions. Doing so will eliminate bias associated with investigator self-interest and ensure subject anonymity.

IV. Drugs/Substances/Devices

- a. Drugs will not be used in this trial. Instead, subjects will be given osteopathic manipulative treatment, BEMER therapy, and placebo light touch.
- b. The device utilized is BEMER Pro set.

Research Participants

The target population is LECOM-Bradenton faculty, staff, osteopathic medical, dental, pharmacy, and master's students who are currently experiencing low back pain. The study will not target participants from a vulnerable or at-risk population. Our target population will be informed via email of the opportunity to participate in the research study and will be given contact information to confirm eligibility with a study coordinator.

I. Inclusion

- a. LECOM-Bradenton faculty, staff and Students currently enrolled in LECOM-Bradenton's osteopathic medical program, pharmacy program, dental program, and master's program who are currently experiencing low back pain will be approached for recruitment.

II. Exclusion

- a. Subjects will be excluded if they are unable to provide informed consent, are currently pregnant, or have a known medical history of current
 - i. Psychiatric conditions
 - ii. Skin disorders or open wounds precluding skin contact
 - iii. Fasciitis or fascial tears
 - iv. Myositis
 - v. Neurological symptoms such as numbness, tingling, weakness in lower extremities
 - vi. Neoplasia
 - vii. Cancer
 - viii. Bone fracture, osteomyelitis, or osteoporosis
 - ix. Coagulation problem
 - x. Deep vein thrombosis
 - xi. Adrenal diseases/syndromes
 - xii. Acute upper or lower respiratory infection
 - xiii. Immunosuppressive syndromes
 - xiv. Radiation or chemotherapy within the past 3 years
 - xv. Lupus
 - xvi. Osteopenia
 - xvii. Congestive heart failure
 - xviii. BMI greater than 30
 - xix. Any other autoimmune disease not stated above
 - xx. Medication changes within the last 4 weeks

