 - xxi. Asthma exacerbations within the last 4 weeks
 - xxii. Immunosuppressive therapy as a consequence of organ transplantation
 - xxiii. Immunosuppressive therapy as a consequence of allogeneic cellular transplants or bone marrow stem cell transplantation

- xxiv. Other conditions often requiring immunosuppressive therapy
- xxv. Anticoagulant therapy
- xxvi. Known sensitivity to the carotid sinus reflex
- b. Subjects will be screened for eligibility based on the inclusion and exclusion criteria described above at the point of subject consent. No protected health information will be collected from subjects who are not eligible to participate in the study.
- c. If subjects develop any of the above issues during the course of the study, they will be removed from the study without penalty and will still receive compensation.

III. Definition of treatment failure or subject removal criteria

- a. Subjects who do not adhere to the full treatment regimen will be removed from the study.
- b. Subjects who experience any adverse effects from treatment, as determined by a licensed osteopathic physician, will be immediately removed from the study. However, we do not anticipate any adverse effects during the study.

Risks and Benefits

I. Risks

- a. Anticipated medical risks**
 - i. After OMT, muscle tenderness and generalized discomfort may be noted 24-48 hours after treatment in a small number of patients.
 - ii. There is little empiric data about the “hazards” to patients of student-performed procedures. Further, this study does not employ any inherently forceful techniques.
 - iii. There are no anticipated adverse effects associated with BEMER therapy.
- b. Steps taken to minimize the risks**
 - i. All Osteopathic Medical students performing osteopathic manipulation will receive additional special training by a licensed osteopathic physician, member of the LECOM-Bradenton OMM Department, and will disclose their true identity to the subjects to avoid any misconceptions that they are licensed physicians. Student-treaters will be critiqued by a physician until they are approved to perform OMT on the subjects.
 - ii. A licensed osteopathic physician will be in the vicinity of the treatment location at all times a treatment is being given.

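### Removing randomised subjects for non-adherence, adverse effects or new exclusion conditions, with no stated follow-up, leaves a completer analysis that can differ by arm

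*Combined protocol and SAP*

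**What the plan says.** Three rules take a randomised subject out of the study, not merely off treatment:

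- Research Participants, III.a: "Subjects who do not adhere to the full treatment regimen will be removed from the study".
- Research Participants, III.b: "Subjects who experience any adverse effects from treatment, as determined by a licensed osteopathic physician, will be immediately removed from the study".
- Research Participants, II.c: for subjects who develop a listed exclusion condition "during the course of the study, they will be removed from the study without penalty and will still receive compensation". The list includes "Medication changes within the last 4 weeks" (II.a.xx) and neurological symptoms in the legs (II.a.v).

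Outcomes are collected twice. Under Study Procedures and Timeline, c.iii, subjects fill in the questionnaires at baseline and "will complete the same questionnaires following the completion of the three week treatment".

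The Analysis section (III.a.ii) plans two tests: "Paired T-tests (N~10 subjects) to investigate the changes in low back pain after each treatment protocol" and "One-Way ANOVA to investigate any statistically significant differences between the means of each of the 4 experimental groups". It names no analysis set, gives no rule for missing data, and does not say whether removed subjects are still asked for the final questionnaires. The consent form (Appendix B) was not in the text available for this review, so nothing is concluded about it.

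Payment and Costs, I, guarantees the $50 to subjects who cannot finish because of adverse events and withholds it from noncompliant subjects.

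**The concern.** Randomisation protects the four-arm comparison only if everyone randomised is measured and analysed in the assigned arm. A paired t-test needs a second questionnaire, and that questionnaire is tied to completing treatment. Followed as written, the rules therefore produce a completer analysis.

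Removal could well be related to how a subject is doing. A worsening back may bring a medication change, leg symptoms or missed sessions; an improving one may also lead someone to stop attending. Either way, the within-arm changes and the between-arm differences would mix treatment effect with selection. Without week-3 data on the removed subjects, the final data could not show by how much. Each loss also shrinks arms of only about 10.

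Two definitions that decide who is removed are missing: whether a rescheduled session counts as adherence, and whether starting a pain killer counts as a medication change.

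**Working it through.** **Planned size.** N~10 per paired test times 4 arms = 40, which matches the 40 subjects in the budget. No alpha, power, effect size, SD or dropout allowance is stated, so N~10 cannot be derived further. The allocation ratio is not given; equal arms are assumed.

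**Sessions needed for full adherence** (Study Procedures and Timeline, a.i):

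- OMT: 3 × 3 = 9.
- BEMER: 5 × 3 = 15.
- OMT+BEMER: 9 + 15 = 24 procedures, or 15 visits if both are given on the same days.
- Placebo: "Finally, subjects in the Placebo group will receive the light touch and BEMER sham treatments at same intervals as the corresponding experimental groups". This is read as the same 9 + 15, although the wording leaves room for doubt.

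**Model (all rates assumed).** Two-sided 5% tests, 10 per arm, no true effect. The change score is N(0,1), higher being worse. A removal score has correlation r with the change score, and a subject is removed when it exceeds the cut-off z for the arm's removal rate p. The mean of those left then looks better by

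shift = r·φ(z)/(1−p).

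Type I error comes from 40,000 simulated null trials per scenario. Here r = 0.5 is a moderate link, and r = 1 (removal depends on outcome alone) is an upper bound.

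**(a) 20% removed in every arm.** Paired t-test: 7.2% (r = 0.5) and 14.7% (r = 1). ANOVA: 4.8% and 4.9%, unaffected because the selection is equal.

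**(b) 20% removed in the two OMT arms only**, to represent the adverse-effect rule. Here φ(z) = 0.280, so the shift is r × 0.280/0.80 = 0.18 SD (r = 0.5) and 0.35 SD (r = 1) in favour of OMT. ANOVA: 6.4% and 11.4%.

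**(c) Adherence rule alone**, each session missed independently with probability 2% and not made up. Removal is 1 − 0.98^k.

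| Sessions k | Removed | φ(z)/(1−p) |
|---|---|---|
| 9 | 17% | 0.30 |
| 15 | 26% | 0.44 |
| 24 | 38% | 0.62 |

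- *Shared visits* (k = 9, 15, 15, 15): expected losses 1.7 + 2.6 + 2.6 + 2.6 = 9.5, so about 30 of 40 are left. The shift favours Placebo over OMT by r × (0.44 − 0.30) = 0.07 and 0.14 SD. ANOVA: 4.9% and 6.1%.
- *Separate sessions* (k = 9, 15, 24, 24): expected losses 1.7 + 2.6 + 3.8 + 3.8 = 11.9, so about 28 of 40 are left. The shift favours Placebo over OMT by r × (0.62 − 0.30) = 0.16 and 0.32 SD, with none for OMT+BEMER against Placebo. ANOVA: 6.0% and 10.7%. The paired t-test in the arms losing 38% reaches about 10% and 44%.

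Scenarios (b) and (c) point in opposite directions, and all signs reverse if improvers are the ones who stop attending.

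**Precision, even with r = 0.** The two-arm difference detectable with 80% power (noncentral t, two-sided 5%) is 1.32 SD at 10 vs 10, 1.57 SD at 8 vs 7 (shared visits) and 1.65 SD at 8 vs 6 (separate sessions).

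**The case against.** The text gap is not in dispute; the size is.

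- With BEMER five times a week, OMT could fall on the same days, so the 15-visit case is the more plausible one. There the ANOVA is almost unaffected. This stands.
- Scenario (b) assumes that 20% of the OMT arms are removed, yet tenderness is expected in few patients and removal needs a physician's determination. With 5–10% removed in those arms, the ANOVA error rate is 5.1–5.5% at r = 0.5 and 5.7–6.7% at r = 1. This stands too.
- The large figures need r = 1. Sessions missed because of class or work would be far less related to pain. At r = 0.5 the ANOVA stays at about 5–6%, and shifts of 0.16–0.18 SD are small beside a standard error of √(2/10) = 0.45 SD for a two-arm difference.
- Sessions are individually scheduled, so make-up sessions may be possible; the model allows none.

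These points argue for modest expected bias in the ANOVA. They do not supply an analysis set or follow-up after removal. Nor do they help the paired tests, which are inflated even when removal is equal across arms. That unequal removal will occur is an inference from session counts and expected tenderness, not a figure in the documents.

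**Conclusion.** The concern holds and should be fixed. It is firmly established that three rules remove randomised subjects, that the only post-treatment assessment follows completed treatment, and that the text reviewed names neither an analysis set nor follow-up after removal.

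The size is illustrative only, since every removal rate and every r is an assumption. At r = 0.5 the inflation is small for the ANOVA (5–6%) and moderate for the paired tests (7% with 20% removed, about 10% with 38% removed). At the r = 1 bound the ANOVA reaches about 11%, and the paired tests 15% and 44% at those same removal rates. The net direction cannot be predicted. The loss of precision needs no assumption about r, only that subjects are lost.

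**What to change.** Leave the treatment-stopping decisions as they are, and state in the protocol that stopping treatment does not end follow-up. Then:

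1. Ask every randomised subject who still consents for the VAS, Oswestry and SF-12 at 3 weeks.
2. Make the primary analysis set all randomised subjects, in the assigned arm. State in advance how non-responders are handled, for example by repeating the comparison over a range of assumed changes for them.
3. Report removals by arm and reason.
4. Keep the fully adherent set as a sensitivity analysis, and define for it whether a rescheduled session counts. State whether a new pain killer is a medication change.
5. Keep the payment already guaranteed after adverse events or new conditions, and extend the $50 to non-adherent subjects who return the final questionnaire.
6. Reconcile the passage expecting tenderness after OMT (Risks and Benefits, I.a.i) with those anticipating no adverse effects (Analysis, III.a.iii; Research Participants, III.b).

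The cost is a protocol amendment with IRB approval, a reversal of the rule that noncompliant subjects go unpaid, and one set of questionnaires per removed subject: about 10 to 12 of 40 at the assumed 2% miss rate, more if attendance is worse. Payment stays within the $2,000 already budgeted (40 × $50).

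The downside is that the estimate describes being assigned a regimen, not completing it, and some removed subjects may still not reply. Inflating the sample size instead would restore power but would not remove the selection.

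### Subjects with an adverse effect or a new exclusion condition are removed from the study, not only from treatment, so their final scores would probably be lost

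*Combined protocol and SAP*

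**What the plan says.** Three rules in the Research Participants chapter take a randomised subject out of the study.

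- III.b, adverse effects: "Subjects who experience any adverse effects from treatment, as determined by a licensed osteopathic physician, will be immediately removed from the study". It continues: "However, we do not anticipate any adverse effects during the study".
- II.c, new exclusion conditions: "If subjects develop any of the above issues during the course of the study, they will be removed from the study without penalty". The list it refers to includes lower-limb numbness, tingling or weakness (II.a.v) and "Medication changes within the last 4 weeks" (II.a.xx).
- III.a, non-adherence: "Subjects who do not adhere to the full treatment regimen will be removed from the study".

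Outcomes are collected twice. Under Methodology II.c.iii, subjects answer the questionnaires before the study starts and "will complete the same questionnaires following the completion of the three week treatment". The primary outcome is the questionnaire rating before and after treatment. The within-group analysis is "Paired T-tests (N~10 subjects) to investigate the changes in low back pain after each treatment protocol", and a one-way ANOVA compares the four groups (Methodology III.a.ii).

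The early stopping rules (Methodology III.a.iii) list any adverse effect determined by the attending physician and say that none is anticipated. Under Risks and Benefits, I.a.i, one reaction is foreseen: "After OMT, muscle tenderness and generalized discomfort may be noted 24-48 hours after treatment in a small number of patients". I.a.iii anticipates none with BEMER. For subjects who cannot finish because of an adverse event, Payment and Costs I.b provides continued compensation. The available text gives no early-termination assessment, follow-up after removal, analysis population or method for missing scores.

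**The concern.** Stopping treatment after an adverse effect is a safety decision. Ending outcome collection is a separate one, and III.b and II.c combine the two. A randomised subject's outcome is then discarded because of something that happened after treatment began, so the groups compared may no longer be the groups randomised. In arms of about ten, each loss is about a tenth of an arm, and no replacement is described. The loss is also avoidable, because the questionnaire that would be missed is already scheduled.

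**Working it through.** **1. Does removal imply a missing final score?** Taken together, the rules point that way.
- III.b and II.c say removal from the study, and III.b says at once.
- The only post-treatment score comes after the three-week course.
- A paired change needs both scores, so a baseline score alone does not enter the paired t-test.
- Reading III.b as a stop to treatment only does not help. That subject would not complete the regimen, and III.a removes such subjects without exempting those stopped by a physician.

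The protocol never states that the score is not collected. Hence probably, not certainly.

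**2. Planned size.** Four groups of about 10 give 4 × 10 = 40, which agrees with the 40 subjects in the budget (40 × $50 = $2,000). No alpha, power, effect size, SD or dropout rate is stated, so there is no sample-size calculation to reproduce.

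**3. Precision within one arm.** The 95% half-width in SD units is t(0.975, n−1)/√n.
- n = 10: 2.262/3.162 = 0.7154
- n = 9: 2.306/3 = 0.7687, which is 7.5% wider
- n = 8: 2.365/2.828 = 0.8360, which is 16.9% wider

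This assumes the SD is unchanged.

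**4. Precision between two arms.** For the unadjusted 95% interval with variance pooled over four arms, the half-width in SD units is t(0.975, N−4) × √(1/n₁ + 1/n₂).
- 10 and 10, N = 40: 2.028 × √0.2 = 2.028 × 0.4472 = 0.907
- 9 and 10, N = 39: 2.030 × √(1/9 + 1/10) = 2.030 × 0.4595 = 0.933, which is 2.8% wider
- 8 and 10, N = 38: 2.032 × √(1/8 + 1/10) = 2.032 × 0.4743 = 0.964, which is 6.3% wider

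**5. How often.** The documents give no rate. The table assumes per-subject removal probabilities p. Expected removals among about 20 subjects in the two OMT arms are 20p, and the chance of at least one in an arm of 10 is 1 − (1−p)^10.

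| Assumed p | Expected among 20 | At least one in 10 | Two or more in 10 |
|---|---|---|---|
| 2% | 0.4 | 18% | 1.6% |
| 5% | 1.0 | 40% | 8.6% |
| 10% | 2.0 | 65% | 26% |

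These figures apply only if the physician counts every such reaction as an adverse effect. If not, removals may be nil.

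**6. Bias.** Suppose k of 10 are removed and would have improved D mm less on the 100 mm VAS than those retained. The retained mean minus the full-arm mean is then kD/10. With D assumed from −30 to +30 mm, one removal shifts the arm mean by −3 to +3 mm and two by −6 to +6 mm. D = 0 gives no shift. The expected shift is about pD, so at most about 0.10 × 30 = 3 mm either way at the highest assumed rate. For scale, with an assumed SD of change of 15 to 25 mm, the standard error of a 10-subject arm mean is 15/√10 = 4.7 mm to 25/√10 = 7.9 mm.

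**The case against.** **The trigger may never occur.** The protocol says twice that no adverse effects are anticipated, yet lists post-OMT tenderness among anticipated risks. The statements agree most easily if ordinary tenderness is not an adverse effect. This stands as a limit on frequency. It does not settle the rule, because neither III.b nor the early stopping rule says whether tenderness counts.

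**The randomised comparison suffers less than the within-arm test.** This stands: 2.8% and 6.3% for the between-arm interval, against 7.5% and 16.9% within the arm.

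**III.a is the wider rule.** Non-adherence needs no physician's finding and may remove more people. This also stands. The change proposed here covers only subjects stopped under III.b or II.c and does not cure the removal of other non-adherers.

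**Keeping subjects after a medication change has a price.** If the change is to an analgesic, the VAS and Oswestry section 1, which is worded around pain-killer use, may partly reflect it. This stands and is counted as a cost. The protocol does not say whether II.a.xx covers analgesics.

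**Follow-up might be described elsewhere.** The consent form (Appendix B) was not available for this review and could cover it. Nothing here treats its absence as a fault.

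**Stronger readings.** A reader might infer that the rule makes OMT look better by dropping those who react badly. The documents do not support that: tenderness at 24 to 48 hours may say nothing about the three-week score, and no rate is given. Losses would fall mainly on the two OMT arms only if the physician counts that tenderness. A reader might also take the early stopping rule to mean that one adverse effect ends the trial. Its text does not say whether it applies to a subject or to the whole trial.

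**Conclusion.** The point holds as a worthwhile, inexpensive improvement. As written, III.b and II.c would probably discard the final score of a randomised subject because of an event after randomisation. The number affected is unknown and may be zero, and neither the size nor the direction of bias follows from the documents. Even at the extreme assumed values, the expected shift in an arm mean is smaller than its standard error.

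The loss of precision depends only on the planned arm size, an unchanged SD and the number removed. It is modest for the between-arm contrast and larger for the paired test. These figures do not show that the trial's conclusions would be invalid. The case for change is that outcome collection should not hinge on an undefined judgement about what counts as an adverse effect.

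**What to change.** **Change.**
- Reword III.b along these lines: a subject with a physician-determined adverse effect from treatment stops study treatment at once; unless the subject declines or can no longer consent, the final questionnaires are completed at the planned three-week time and the subject is analysed in the assigned group.
- Apply the same wording to II.c.
- State that III.a does not remove subjects whose treatment was stopped under III.b or II.c.
- State that the early stopping rule (Methodology III.a.iii), applied to an individual, ends that subject's treatment and not outcome collection. Any trial-wide stop remains the physician's decision.
- Report by arm how many subjects stopped and how many have no final score.
- For subjects kept after a medication change, record the change and report a sensitivity analysis without them.

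**Cost.** One small IRB amendment and a short addition to the analysis section. Immediate stopping of treatment is unchanged, the questionnaires are already planned, and compensation already continues (Research Participants II.c; Payment and Costs I.b). Some stopped subjects may decline. Their scores will reflect incomplete treatment, so the comparison becomes one of assigned rather than completed treatment, and the SD may rise. Scores after a medication change may partly reflect the new medication.
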